## Statistical Analysis Plan

The safety population will be used for the descriptive analysis. The CVT-301-003 and CVT-301-009 rollover subjects will be excluded for MMRM analysis.

In addition, the changes in the spirometry values within treatment arm in CT-301-004 (CVT-301 vs Placebo) and differences between the CVT-301-004 treatments (CVT-301 vs Placebo) will be estimated with MMRM. The model will include the treatment group (CVT-301 DL1 or CVT-301 DL2), CVT-301-004 treatment, visit (visits at 1, 3, 6, 9, and 12 months), the stratification variables (Hoehn and Yahr stage and screening FEV1 and/or FEV1/FVC) and the interaction between CVT-301-004 treatment and visit as fixed factors. The baseline spirometry value will be included as a covariate. An unstructured covariance structure will be applied for MMRM. In case the model will not converge with the unstructured covariance structure, the heterogeneous compound symmetry (CSH) or the heterogeneous Toeplitz structure (TOEPH) will be used instead. If the unstructured covariance structure will be used, the denominator degrees of freedom will be computed using the Kenward-Roger method. In case of other covariance structures, the BETWITHIN option will be used for the denominator degrees of freedom. The least square (LS) mean, standard error, and LS mean difference for the changes from baseline within CVT-301-004 treatment, and between the CVT-301-004 treatment arm at each visit; along with the 95% confidence interval (CI) will be provided in a table. CVT-301-004 treatment arm difference will be assessed with a 2-sided alpha level of 0.05, unless specified otherwise.

The SAS code planned for the analysis is outlined below.

```
proc mixed data=&data;
class pdsevbl fevlbl trta stdygrp avisit usubjid;
model chg=base pdsevbl fevlbl stdygrp avisit trta stdygrp*avisit /
ddfm=kr;
repeated avisit / subject=usubjid(stdygrp) type=un;
lsmeans stdygrp*avisit / cl pdiff;
ods output Diffs=DIFF_MI LSMeans=LSM_MI tests3=tests ;
run;
```

The CVT-301-004 rollover patients in safety population will be used for the analysis.

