12.3. Definition of Baseline

For all statistical analyses, except for assessments of withdrawal symptoms, the visit at which the CVT-301 treatment is initiated will be used as the baseline. This will be TV1 from the [CVT-301-](#)

004 study for actively treated patients, i.e. randomized to DL1 or DL2. However, TV1 of the CVT-301-004E study will be used as the baseline for all placebo-treated subjects from study CVT-301-004, for patients from study CVT-301-009, and for patients from the observational arm of study CVT-301-005 and other CVT-301 naïve patients.

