12.5. Safety Analysis

The disposition of the patients will be summarized by tabulating the number of screened, randomized, completed, and discontinued patients. The reasons for premature discontinuations will be tabulated.

The extent of exposure to study treatment will be summarized for each dose level. For the patients who received CVT-301 treatment in the CVT-301-004 study, the total exposure will be the sum of exposure in the CVT-301-004 study and the CVT-301-004E study.

All AEs will be coded using the Medical Dictionary for Regulatory Activities (MedDRA) dictionary. The TEAEs (i.e., events which start or worsen during the study treatment) will be tabulated by treatment group, system organ class, and preferred term. Both patient and event counts will be calculated. In addition, the TEAEs will be evaluated by seriousness, severity, and causality to the study treatment. The AEs leading to a premature discontinuation or dose adjustment will also be summarized. The AEs will be summarized by dose level (CVT-301 DL1 or CVT-301 DL2). Descriptive statistics will be used to describe the overall incidence of TEAE normalized for duration of exposure (number of TEAEs divided by the total exposure to CVT-301 measured as patient years). Furthermore, the time of onset of the TEAEs will be summarized.

For vital signs, ECG parameters, spirometry, the changes from pre-dose to post-dose assessments of the corresponding day will be calculated and compared between the treatment groups using descriptive statistics. For spirometry and safety laboratory variables, the differences in pre-dose values between study days will be described. Furthermore, the changes in the spirometry values and difference between the groups (DL1/DL2 or patients treated with CVT-301/placebo in CVT-301-004) will be estimated using a Mixed Model for Repeated Measurements (MMRM) similar to the one used for the efficacy variables. The proportions of patients meeting ATS quality criteria (and also for those ‘rejected’) will be summarized. Changes from baseline to follow-up in the rating scales for assessing suicidality, somnolence, and impulse control disorders will be summarized descriptively.

At least the following variables will be analyzed:

- Vital signs: standard and orthostatic systolic and diastolic BP and HR.

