## Statistical Analysis Plan

### Baseline

Baseline is defined as the last non-missing assessment before the first dose of CVT-301 in study CVT-301-004 for the patients who received CVT-301 in CVT-301-004 and as the last non-missing assessment before the first dose of CVT-301 in CVT-301-004E for the rest of the patients.

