## Statistical Analysis Plan

### 8. EFFICACY

The efficacy evaluation defined below includes data from the patients who were previously enrolled in the CVT-301-004 study and for the CVT 301 naïve patients (including patients from CVT-301-005 observational arm). The data from patients who were enrolled to study CVT-301-003 or CVT-301-009 will not be included in the efficacy summaries and will be listed only.

In general, for the purpose of the efficacy analyses, the visits will be pooled as follows:

Treatment/study group	Study CVT-301-004				Study CVT-301-004E			
	Baseline visit	Week 4 visit	Week 8 visit	Week 12 visit	Baseline visit	Month 1 visit	Month 3-9 visits	Month 12 visit
CVT-301-004, CVT-301 group	Baseline	Month 1	not used	Month 3	not used	not used	Months 6-12	not used
CVT-301-004, placebo group	not used	not used	not used	not used	Baseline	Month 1	Months 3-9	Month 12
CVT-301 naïve patients	NA	NA	NA	NA	Baseline	Month 1	Months 3-9	Month 12
CVT-301-005, Observational, Arm	NA	NA	NA	NA	Baseline	Month 1	Months 3-9	Month 12

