## Statistical Analysis Plan

### 9. SAFETY

The population used for safety analyses will be the Safety Population. The analyses are outlined below. The safety evaluation defined below includes data from all patients included in the Safety population.

For the statistical analysis of the spirometry data, the visits will be pooled as described in [Section 8](#). Otherwise, all safety data will be presented in the summaries,

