#### 9.1. SPIROMETRY

For CVT-301-naïve patients and [CVT-301-009](#) patients, spirometry will be assessed at the neurology sites for screening and TV1 and the pulmonary sites will be exclusively responsible for the conduct of spirometry after TV1 (within 2 weeks prior to the 3-, 6-, 9-, and 12-month visits, and 4 to 5 weeks following completion of Treatment Visit 6 [TV6]). For patients from [CVT-301-004](#), spirometry will be assessed at the neurology sites at TV1, and the pulmonary sites will be exclusively responsible for the conduct of spirometry after TV1 as described for the CVT-301-naïve patients. Spirometry data obtained in the study site will reviewed by a central spirometry laboratory (Biomedical Systems, Inc.) which will provide a quality over read of all evaluations based on acceptability and repeatability metrics in accordance with ATS criteria. FEV1, FVC and FEV1/FVC ratio will be recorded from the single “best test” (based on effort with highest summed FEV1 and FVC). Variables will include the absolute FEV1, FVC, and FEV1/FVC ratio and FEV1 and FVC expressed as % of predicted value.

The variables from pulmonary laboratory will include the FEV1, FVC, FEV1/FVC ratio, DLCO, IVC, SVC and VA. FEV1 and FVC expressed as % of predicted value, predicted DLCO, hemoglobin (Hb) adjusted predicted DLCO, and DLCO expressed as % of these predicted values will be calculated per the method in [section 6.2](#). The following analysis will be performed:

All the parameters collected at the pulmonary laboratory as well as the % of predicted DLCO and % of Hb adjusted predicted DLCO will be summarized descriptively by treatment group and overall. In addition, the data will be summarized by treatment/study group.

- Change from baseline to other visits for each parameter.
- Number and percentage of patients with FEV1/FVC < 60% and <70% by visit
- DLCO data will also be provided to indicate whether specific determinations met American Thoracic Society (ATS) quality criteria. The proportion of DLCO/spirometry data measurements meeting or not meeting ATS quality criteria will be summarized by treatment group and overall.

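### The rollover spirometry model labelled CVT-301 versus placebo compares two groups both taking CVT-301 at roughly matched exposure, and its Month 1 difference cannot be estimated

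*SAP*

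**What the plan says.** SAP 9.1 plans two spirometry MMRMs. The second uses CVT-301-004 rollover patients only and is the one in which "differences between the CVT-301-004 treatments (CVT-301 vs Placebo) will be estimated with MMRM". Its visit factor has levels at Months 1, 3, 6, 9 and 12. Arm differences with 95% confidence intervals are promised for every visit, and "CVT-301-004 treatment arm difference will be assessed with a 2-sided alpha level of 0.05".

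Three other provisions determine what enters that model.

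- **Baseline.** SAP 6.2: "Baseline is defined as the last non-missing assessment before the first dose of CVT-301 in study CVT-301-004 for the patients who received CVT-301" in that study. All other patients take their last value before the first dose in CVT-301-004E. Protocol 12.3 agrees: "TV1 of the CVT-301-004E study will be used as the baseline for all placebo-treated subjects from study CVT-301-004".
- **Visit pooling.** SAP 9: "For the statistical analysis of the spirometry data, the visits will be pooled as described in" Section 8. In that table the former CVT-301 arm contributes 004 Week 12 as Month 3 and its 004E Months 3-9 as Months 6-12; its 004E Month 12 is dropped. In the row "CVT-301-004, placebo group" no 004 visit is used, and the 004E visits keep their own month labels.
- **Test schedule.** SAP 9.1 gives the pulmonary sites "spirometry after TV1 (within 2 weeks prior to the 3-, 6-, 9-, and 12-month visits", plus a test 4 to 5 weeks after TV6. Protocol 11.1.6 likewise leaves all later tests to the laboratory visits. The TV2 (Month 1) procedures in Protocol 10.1.3.5 and Appendix 6 contain no spirometry.

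The Protocol's own commitment, in 12.5, is that the "difference between the groups (DL1/DL2 or patients treated with CVT-301/placebo in CVT-301-004) will be estimated". It does not ask for a test of this difference.

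**The concern.** The model serves a stated safety objective: comparing spirometry between patients who had CVT-301 and patients who had placebo in CVT-301-004 (Protocol 6, SAP 3.3). It is the only modelled contrast for that objective. The first model carries treatment/study group only as a main effect and requests least-squares means by dose level and visit.

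A contrast labelled CVT-301 versus placebo, with a 0.05 criterion, looks like a test of the drug against placebo. If both arms are on drug for about the same time, a result near zero is expected by construction, even when CVT-301 lowers FEV1. In a study whose main purpose is pulmonary safety, such a null could be taken as reassurance that the model cannot give.

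**Working it through.** The plan gives no sample size, power or effect size for this contrast, so there is no stated figure to reproduce. Two things can be checked: exposure at each model visit, and estimability.

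**Exposure.** Inputs are the pooling table (SAP 8), visit weeks (SAP 3.8: TV3 12, TV4 24, TV5 36, TV6 52) and Protocol 10.1.3.9 (TV6 at 56 or 60 weeks). A patient seen at 60 weeks after the 4-week holiday has 60 - 4 = 56 weeks on drug.

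| Model visit | Former CVT-301 arm, weeks on drug | Former placebo arm, weeks on drug |
|---|---|---|
| Month 3 | 12 (004 Week 12) | 12 |
| Month 6 | 12 + 12 = 24 | 24 |
| Month 9 | 12 + 24 = 36 | 36 |
| Month 12 | 12 + 36 = 48 | 52 (SAP) or about 56 (Protocol) |

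These are nominal. They ignore the ±14-day windows at TV3 to TV6, testing up to 2 weeks before the visit, and the 1- to 14-day gap between studies. A 28-day holiday after TV4 changes individual values: 36 - 4 = 32 at Month 9 for a former placebo patient, and 48 - 4 = 44 at Month 12 for a former CVT-301 patient.

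Write d(t) for the mean drug effect after t weeks, with the same time course in both arms. The drug component of the contrast is d(t, former CVT-301) - d(t, former placebo). When the two times agree it is zero, however large d is. CVT-301 versus placebo at Week 12 would be d(12), and no term in the model estimates that.

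**Illustration of the Month 12 residual.** Assume a shared linear loss of L mL per 52 weeks; L is not in the documents. Former CVT-301 minus former placebo = L × (weeks in former placebo arm - weeks in former CVT-301 arm) / 52.

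- 48 v 52, L = 100: 100 × 4/52 = +7.7 mL (L = 50: +3.8; L = 200: +15.4).
- 48 v 56, L = 100: 100 × 8/52 = +15.4 mL (+7.7; +30.8).
- 44 v 56, L = 100: 100 × 12/52 = +23.1 mL (+11.5; +46.2).
- For comparison, drug against placebo at Week 12, L = 100: -100 × 12/52 = -23.1 mL.

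The Month 12 sign makes the arm exposed first look slightly better under a harmful cumulative effect. At Month 9, a holiday in a former placebo patient acts the other way: 100 × (32 - 36)/52 = -7.7 mL. Holiday figures apply to individual sub-study patients, so group means move less.

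**Estimability.** The planned fixed effects are intercept, baseline, two strata, prior arm, visit, dose level, and prior arm by visit. With all ten arm-by-visit cells filled, the rank is 1 + 1 + 2 + 1 + 4 + 1 + 4 = 14, and all five differences are estimable. A difference is estimable only if adding its contrast row leaves the rank unchanged.

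- Former-placebo Month 1 cell empty: rank 13. Month 1 is not estimable; the other four differences are.
- Month 1 empty in both arms: rank 12. Month 1 is again not estimable.

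The Month 1 result therefore does not depend on what 004 collected. The early-termination rule in SAP 6.4 cannot fill the cell, because it moves data only to scheduled time points.

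The same reasoning applies at Month 3. The former CVT-301 value there is 004 Week 12, and these documents do not show the 004 spirometry schedule or laboratory setting. If no comparable test exists, Month 3 is not estimable either. Months 6, 9 and 12 use scheduled 004E laboratory tests in both arms and are estimable, given each patient's baseline value.

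**The case against.** The strongest reply is that the label only names prior-treatment groups. SAP 3.3 describes the second group as CVT-301 patients who had placebo in the parent study, the factor is called CVT-301-004 treatment, and the table titles repeat that name with the rollover restriction. The Protocol lists no reference therapy. On this reading the model does what it says, and the calculation stands. That much is correct.

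The plan also sets no margin or decision rule, reports confidence intervals, and provides descriptive summaries by treatment/study group. The 4-week Month 12 mismatch under the SAP schedule is no wider than a ±14-day visit window. These points also stand, and they limit the matter to interpretation and one empty cell.

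They do not remove it. SAP 9.1 nowhere says that the contrast is made at matched time on drug. It adds a 0.05 assessment that Protocol 12.5 does not call for, and it promises a Month 1 difference that cannot exist.

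A reader might infer that the sponsor plans to conclude no pulmonary difference from placebo. No passage says so. A reader might also infer that the pulmonary safety evaluation as a whole fails; the primary objective concerns change within CVT-301-treated patients and does not use this contrast.

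**Conclusion.** Wrong as written, and worth fixing. The rollover contrast is a consistency check by prior CVT-301-004 treatment at approximately matched time on CVT-301. It cannot inform CVT-301 versus placebo, because no on-placebo visit enters it and a common effect largely cancels. Nominal exposure matches at Months 3, 6 and 9 and differs by 4 to 8 weeks at Month 12, before windows, early testing and holidays. The cancellation argument assumes the same effect time course in both arms. Differences arising from selection into rollover or from measurement setting would not cancel.

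The Month 1 difference is not estimable. Months 6 to 12 are; Month 3 is conditional on 004 data not shown here, so it would be too strong to call every visit from Month 3 onward estimable. The mL figures illustrate direction and rough size under assumed slopes and are not bounds.

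**What to change.** In SAP 9.1:

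1. Relabel the second model as a consistency comparison by prior CVT-301-004 treatment at approximately matched time on CVT-301, and state that it does not estimate CVT-301 versus placebo.
2. Replace the 0.05 assessment with estimates and 95% confidence intervals.
3. Remove Month 1 from the contrast, and make Month 3 conditional on comparable 004 Week 12 spirometry.
4. State the Month 12 exposure mismatch: about 48 weeks against 52 or 56.

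Carry the description into the matching table titles or footnotes: 14.3.4.5.1.4.2, .5.2, .6.2, .11.2, .12.2 and .13.2, and 14.3.4.5.2.4.2, .5.2 and .6.2. The cost is SAP wording and a small change to the reported contrasts. SAP 2 allows updates until database lock.

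An exploratory model on calendar time since 004 randomisation, using the on-placebo 004 visits, is optional. It depends on what spirometry 004 collected, applies only to completers who rolled over, and departs from the Protocol 12.3 baseline, so it would need listing in SAP 11. Its precision for an early-versus-delayed-start difference would be low. With an assumed SD of 0.21 L and 120 against 60 patients, SE = 210 × √(1/120 + 1/60) = 33.2 mL; assumed SDs of 0.15 to 0.25 L and groups of 120/60 to 200/100 give 18 to 40 mL. The illustrative 12-week difference above is 23.1 mL.

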### Sensitivity analyses of the spirometry data

The following sensitivity analysis will be performed for FEV1, FEV1/FVC and DLCO assessments.

- MI analysis: MI techniques based on Pattern Mixture Models (PMM) will be applied (Ratitch et al., 2011) as a further sensitivity analysis in the Safety population. This methodology will structure data based on missing data patterns. The method will be based on a missingness pattern having a monotone structure, i.e. if among the observations over time one data value is missing, all other values after this missing

## Statistical Analysis Plan

value will also be treated as missing. For patients with intermittent missing values, before performing MI based on the PMM, it will be necessary to create a monotone missingness pattern. Intermittent missing values will be imputed using the Markov Chain Monte Carlo (MCMC) methodology which assumes a multivariate normal distribution over all variables included in the imputation model. The MI procedure in SAS will be used for this purpose and this first MI step is planned to be repeated 100 times, creating several different datasets with a monotone missing data structure. Seed value of 201508 will be used in the MI procedure. The imputation is based on the missing at random (MAR) assumption, i.e. the missing data are assumed to follow the same model as the other patients in their respective treatment group that have complete data.

After this, the remaining missing data can be imputed using a method for monotone missingness, also based on the MAR assumption. Thus, for each of the created datasets with a monotone missing data pattern, the MI procedure in SAS will be used to impute missing values based on a sequential procedure reflecting the monotone missing data pattern. Patients with the first missing value occurring at visit at Month 1 will have their missing Month 1 value replaced by an imputed value from a regression model with treatment group, treatment/study group, baseline spirometry value, the stratification factors and the interaction between the treatment group and visit as explanatory variables. In the next step, patients with their Month 3 value missing will have their missing Month 3 value replaced by an imputed value from a regression model with treatment group, treatment/study group, baseline spirometry value, stratification factors, the interaction between the treatment group and visit and the Month 1 value as explanatory variables. Similar procedure will be used to replace the missing values at Month 6, 9 and 12.

The imputed datasets generated with the approach described above do contain only non-missing values and are used as input in the model for the primary endpoint. MMRM models similar as described above will thus be run on each of the generated imputed datasets and the difference between the treatment groups will be estimated. The MMRM model will be similar to the primary analysis. Finally, the MIANALYZE procedure in SAS will be applied to combine the results from these several datasets to derive an overall estimate of the within-group changes and treatment group differences. Estimates and corresponding 95% confidence intervals will be calculated.

The following summary will be performed on the neurology sites data.

- Change from baseline to other visits for each parameter. The baseline is defined as the last arrival assessment before the first dose of inhaled CVT-301. If the Arrival value is missing, the last available value in ON state before the first dose

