10.1.5. Early Withdrawal Visit

Patients who withdraw prematurely will complete the TV6 assessments (see [Section 10.1.3.9](#)), except for the pre-TV6 DLco and spirometry assessments, at the time of withdrawal. In addition, patients will be scheduled the DLco and spirometry visit 4 to 5 weeks after completion of the Early Withdrawal Visit. The DLco and spirometry assessments should be performed in an ON state (as reported by the patient to the pulmonary technician) in the pulmonary function facility. As part of the procedure, a slow vital capacity maneuver will be first, followed by DLco, and then spirometry. Patients who withdraw prematurely and prior to participating in the sub-study to assess potential withdrawal symptoms will complete the withdrawal assessments during the 28 days following completion of the TV6 assessments (see [Section 10.1.4](#)).

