## Statistical Analysis Plan

### 4. ENDPOINTS

#### 4.1. PRIMARY ENDPOINT

The primary endpoints related to the primary objective of the study are the pulmonary safety measures, FEV1, FVC and FEV1/ FVC ratio, assessed over a 12 month period. FEV1, FVC and FEV1/FVC ratio will be recorded from the single “best test” (based on effort with highest summed FEV1 and FVC). Variables will include the absolute FEV1, FVC, and FEV1/FVC ratio and FEV1 and FVC expressed as % of predicted value. Changes from baseline (TV1) for each variable will be calculated at each subsequent visit.

Percent Predicted =  $100 * (\text{Observed}) / \text{Predicted}$ , where predicted values are calculated using the formulae by [Hankinson et al \(Spirometric Reference Values from a Sample of the General U.S. Population, 1999\)](#):

Caucasian males  $\geq 20$  years of age:

- FVC predicted =  $-0.1933 + 0.00064 * \text{age} - 0.000269 * \text{age}^2 + 0.00018642 * \text{height}^2$
- FEV1 predicted =  $0.5536 - 0.01303 * \text{age} - 0.000172 * \text{age}^2 + 0.00014098 * \text{height}^2$

Caucasian females  $\geq 18$  years of age:

- FVC predicted =  $-0.3560 + 0.01870 * \text{age} - 0.000382 * \text{age}^2 + 0.014815 * \text{height}^2$
- FEV1 predicted =  $0.4333 - 0.00361 * \text{age} - 0.000194 * \text{age}^2 + 0.00011496 * \text{height}^2$

, Please see Hankinson et al (1999) for formulae for other races and age categories

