## Statistical Analysis Plan

- For the primary analysis of spirometry and selected efficacy endpoints, likelihood-based modeling approach will be used to handle incomplete data. For this purpose, Mixed Model for Repeated Measures (MMRM) will be applied (see [Section 8.1.](#))
- Sensitivity analysis for spirometry and selected explorative efficacy endpoints will be conducted using the Multiple Imputation (MI) approach, i.e. by replacing each missing value with a set of plausible values that represent the uncertainty about the right value to impute, see [Section 9.1.](#)
- For the binary explorative efficacy endpoints, sensitivity analyses will be conducted using worst case imputation, where visits with missing data are counted as non-resolved (primary method), see [Section 8.1.](#)
- For AEs, the overall incidence of TEAEs, normalized for duration of exposure will be calculated to account for the shorter follow-up time in patients who discontinue the study prematurely, see [Section 9.4.](#)

The Safety and ITT population will be used for the analysis of the primary and secondary endpoints. This population includes all patients enrolled to study CVT-301-004E who received at least 1 dose of inhaled CVT-301, regardless of whether they have post-baseline data or not for the variable in question. The patients with no post-baseline data will not contribute to the analyses performed with the MMRM approach, but they do contribute to the sensitivity analyses using the MI approach. Due to this, no additional population, like a modified ITT population including only the patients with post-baseline will be defined.

Safety data (other than the primary endpoint) will not be subjected to any imputation and will be summarized on an observed case basis.

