### Sensitivity analyses of the efficacy data

The following sensitivity analysis will be performed for the daily OFF time efficacy endpoint.

- MI analysis: MI techniques based on Pattern Mixture Models (PMM) will be applied ([Ratitch et al., 2011](#)) as a further sensitivity analysis in the ITT population. This methodology will structure data based on missing data patterns. The method will be based on a missingness pattern having a monotone structure, i.e. if among the observations over time one data value is missing, all other values after this missing value will also be treated as missing. For patients with intermittent missing values, before performing MI based on the PMM, it will be necessary to create a monotone missingness pattern. Intermittent missing values will be imputed using the Markov Chain Monte Carlo (MCMC) methodology which assumes a multivariate normal distribution over all variables included in the imputation model. The MI procedure in SAS will be used for this purpose and this first MI step is planned to be repeated 100 times, creating several different datasets with a monotone missing data structure. Seed value of 201508 will be used in the MI procedure. The imputation is based on the missing at random (MAR) assumption, i.e. the missing data are assumed to follow the same model as the other patients in their respective treatment group that have complete data.

After this, the remaining missing data can be imputed using a method for monotone missingness, also based on the MAR assumption. Thus, for each of the created datasets with a monotone missing data pattern, the MI procedure in SAS will be used to

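### The spirometry imputation labelled pattern-mixture assumes MAR at both steps, so no planned analysis shows how the FEV1 change would move if patients worsened after their last measurement and then left

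*SAP*

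**What the plan says.** SAP 4.1 names the primary endpoints as "FEV1, FVC and FEV1/ FVC ratio, assessed over a 12 month period". For the primary spirometry analysis, SAP 6.3 states that a "likelihood-based modeling approach will be used to handle incomplete data", namely the MMRM. The check on it is given in the same section: "Sensitivity analysis for spirometry and selected explorative efficacy endpoints will be conducted using the Multiple Imputation (MI) approach".

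SAP 9.1 sets out that imputation for FEV1, FEV1/FVC and DLCO. It uses the label that SAP 8.1 uses for daily OFF time: "MI techniques based on Pattern Mixture Models (PMM) will be applied". There are two steps. Intermittent gaps are filled by MCMC, and there "The imputation is based on the missing at random (MAR) assumption". What remains, which is dropout, is "imputed using a method for monotone missingness, also based on the MAR assumption". An MMRM like the primary one is then fitted to each completed dataset and the results are combined. In SAP section 14 the three resulting tables (14.3.4.5.1.7, 14.3.4.5.1.14 and 14.3.4.5.2.7) carry MAR in their titles.

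Protocol 10.1.5 has early withdrawals complete the TV6 assessments "except for the pre-TV6 DLco and spirometry assessments, at the time of withdrawal", with a lab visit 4 to 5 weeks later. The MMRM visits in SAP 9.1 are Months 1, 3, 6, 9 and 12, so that later visit is not among them.

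**The concern.** A pattern-mixture label leads the reader to expect that patients who left are allowed to differ from those who stayed in a way the observed data cannot show. Here they are not. Both steps draw missing values from models fitted to the observed data, conditional on dose group, treatment/study group, baseline, strata and earlier visits. That is in substance the assumption under which a likelihood-based MMRM is valid, so close agreement between the two analyses is expected and says nothing about informative dropout.

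This matters because the primary objective is to characterise lung function, and worsening lung function is a plausible reason to stop an inhaled drug. The protocol itself contains one such route. Under Protocol 10.1.3.2 and 10.1.3.3, a patient who meets the post-dose spirometry alert at TV1 is not sent home with drug until the case is reviewed. Those TV1 post-dose values are not in the imputation model. If stopping follows an unmeasured decline, the primary analysis and its only missing-data check will understate the within-group decline together, and nothing planned would show by how much.

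**Working it through.** **1. Is there a non-MAR analysis of spirometry anywhere?**

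- SAP 6.3: worst-case imputation, for binary efficacy endpoints only.
- SAP 9.1: re-analyses in the ATS-quality subset and without patients whose FEV1 CV exceeds 7.5%. These address measurement quality, not dropout.
- SAP 6.4: safety assessments made at the early-termination visit move to the first missed time point. Lab spirometry is not done at that visit, so the rule brings in no lab value.
- No delta, tipping-point or reference-based assumption is given in either document.

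**2. Who is exposed?** After TV1, spirometry is done only at the pulmonary lab, first within two weeks before TV3 (Protocol 11.1.6 and 11.1.7). Patients who start CVT-301 in 004E and leave before that visit contribute no on-treatment lab value. Patients who leave later have earlier lab values, and both the MMRM and the imputation condition on them. For these patients the exposure is decline after the last measurement.

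**3. How much is missing?** SAP 3.5 plans 390 enrolled for about 290 completers and states no dropout rate.

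- Implied non-completion d = 1 − 290/390 = 100/390 = 0.2564. This returns 390 by construction.
- A round 25% gives 290/0.75 = 387, close to the plan. 20% gives 363 and 30% gives 415.

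**4. Shift in the last-visit mean.** If a fraction d of values is imputed and the true values lie δ below the MAR prediction, the mean is too favourable by d × δ. The δ values are assumed; 200 mL is borrowed from the TV1 alert rule for scale only.

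| δ (mL) | all non-completers, d = 0.2564 | d from 0.20 to 0.30 | only 20% of non-completers, 0.2 × 0.2564 = 0.0513 |
|---|---|---|---|
| 50 | 12.8 mL | 10 to 15 mL | 2.6 mL |
| 100 | 25.6 mL | 20 to 30 mL | 5.1 mL |
| 200 | 51.3 mL | 40 to 60 mL | 10.3 mL |

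**5. Scale.** The documents give no SD. With an assumed SD of change of 250 to 350 mL, the 95% CI half-width, 1.96 × SD/√n, is 41 to 57 mL for one dose arm of 145 completers and 29 to 40 mL for all 290.

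**6. Does agreement between MMRM and MAR imputation carry information?** A simulation compared maximum likelihood under monotone dropout (the analogue of an unstructured MMRM) with sequential-regression MI under MAR. All inputs were assumed: 390 patients, 4 visits, SD 300 mL, correlation 0.6, drift −20 mL per visit, 20 imputations and 300 replicates. The log-odds of dropout rose by 0, 0.5 or 1.0 for each SD by which the current, unobserved value was lower.

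| Dropout | True mean (mL) | ML | MAR-MI |
|---|---|---|---|
| not informative | −79.2 | −79.0 | −79.0 |
| moderately informative | −81.1 | −65.4 | −65.5 |
| strongly informative | −78.7 | −41.8 | −41.9 |

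Within a replicate the two methods differed by 1.3 to 1.4 mL on average, while both understated the decline by about 16 and 37 mL in the informative cases.

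**The case against.** Several counter-arguments have force.

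- *A reader might infer that early withdrawals have only the post-withdrawal lab test.* The documents do not support that. Protocol 10.1.5 waives only the pre-TV6 lab test. Anyone who leaves after TV3, TV4 or TV5 should already have lab values, and a decline recorded there is what MAR uses.
- *A reader might infer that the imputation adds nothing.* That goes too far. It runs in the Safety population and includes patients with no post-baseline data (SAP 6.3), while the MMRM excludes CVT-301-003 and CVT-301-009 rollovers (SAP 9.1). It therefore tests sensitivity to population, but not to the missingness assumption.
- *The 13, 26 and 51 mL are upper-end figures.* They apply the shift to every non-completer, although Protocol 8.3 lists reasons such as withdrawn consent and loss to follow-up. The 390 also includes former CVT-301-003 patients. Under the pooling in SAP 8, which SAP 9 applies to spirometry, patients on CVT-301 in study 004 do not use their 004E Month 12 visit, so their dropout after Month 9 leaves no gap in the model.
- *Other tables would help to reveal lung-related dropout.* Withdrawal reasons (SAP 7.1), TEAEs leading to discontinuation (SAP 9.4) and categories of FEV1 change (SAP 9.1) are all planned. They may show that it occurred, but they do not show its effect on the mean.
- *There is no margin or success rule.* This stands. The study describes within-group change, so no conclusion exists that could formally flip.

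**Conclusion.** The point holds for the missingness assumption. Both imputation steps rest on MAR, the model fitted afterwards is like the primary one, and no other planned analysis relaxes that assumption for spirometry. The effect on the within-group FEV1 mean could range from a few millilitres to about 51 mL. The top of that range needs every planned non-completer to be 200 mL worse than MAR predicts. These sizes rest on assumed shifts and on 25.6% as a stand-in for missingness at the last model visit.

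It does not follow that the pulmonary-safety estimate is biased, because the documents do not say why patients will leave. Nor does it follow that the DL1–DL2 comparison is compromised: equal shifts with equal dropout cancel there. With 20% versus 31% dropout and a 100 mL shift, the difference moves by 0.11 × 100 = 11 mL.

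FVC has a wider gap. It is a named primary endpoint, but SAP 9.1 lists it in neither the dose-group MMRM nor the imputation. This is a worthwhile, low-cost improvement, not a fault that invalidates the plan.

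**What to change.** Keep the MAR imputation, call it that, and add a delta-adjusted version to SAP 9.1:

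- In the monotone step, use the MNAR statement in PROC MI to subtract a range such as 50, 100, 150 and 200 mL from imputed FEV1 after withdrawal. State whether a shift at one visit carries into the next visit's regression.
- Add FVC to the MMRM and the imputation. Pre-state shifts in their own units for FVC, FEV1/FVC and DLCO.
- Report how the within-group mean change and its 95% CI move across the range. Do not report a tipping point, as there is no threshold to tip.
- Optionally, apply the shift only to patients who withdrew for adverse events.
- Show the lab value from 4 to 5 weeks after withdrawal as supportive data, marked as off drug.
- Settle the Month 1 imputation step: patients who start CVT-301 in 004E have no lab spirometry scheduled then.

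The cost is SAP wording and a few tables, with no new data. Under SAP section 2, an analysis defined after study 004 is unblinded counts as exploratory, which is acceptable for this purpose. The downside is that the shifts are a judgement, which is why a range is shown.
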